5.7.4 Methods to Minimize Risk

Methods to minimize risks include inclusion and exclusion criteria that recruit only appropriate subjects into the study. Potential subjects who may be at increased risk of experiencing an adverse reaction will not be enrolled.

Study subjects will be monitored post-operatively to assess the surgical site for any acute and chronic adverse reactions to ensure proper medical treatment can be administered. Validated and standardized outcome scales and surveys will be used to collect subjects' data. Experienced orthopedic surgeons will participate as investigators and have experienced staff to perform the study procedures including post-operative rehabilitation.

6.0 Study Objectives & Endpoints

6.1 Study Objectives

The primary objective of this study is to determine whether Subchondroplasty with arthroscopy is superior to arthroscopy alone for treatment of bone marrow lesions in the knee. Superiority will be evaluated in terms of composite clinical success (CCS) requiring freedom from subsequent secondary surgical intervention (SSSI) and among those free from SSSI, a clinically meaningful reduction in self-reported pain based on a validated measure of subject-reported pain. Conditional on showing superiority in terms of CCS, superiority in terms of improved ADL will then be tested as a conditional endpoint.

Secondary objectives include evaluation of other subject-reported outcomes measures; evaluating the safety profile by determining the incidence and time to resolution of post-operative complications and adverse events; comparing the incidence and time to subsequent secondary surgical intervention including re-operation and revision; and evaluating the use of healthcare resources and impact on productivity.

6.2 Primary Endpoint

The primary measure of clinical success is a composite clinical success (CCS) endpoint requiring:

- Freedom from secondary subsequent surgical intervention (SSSI); and
- Among subjects free from SSSI; an improvement in KOOS pain of at least 10 points.

For the purpose of this study, SSSI will include any partial or total joint arthroplasty or any bone grafting or bone substitute procedure in the study knee.

The 10 point threshold is consistent with ICRS recommendations for the use of changes in the KOOS pain score in responder endpoints [11].

6.3 Secondary Endpoints

Secondary endpoints include evaluation of:

- 1) Comparison of mean change in KOOS subscale scores (Pain, ADL, Symptoms, Sports and Recreation, Quality of Life)

- 2) Longitudinal comparison of KOOS subscales over 12 to 24 months post-surgery
- 3) Comparison of mean Numeric Pain, EQ-5D and Global Satisfaction scores, where available
- 4) X-ray evaluation of joint space narrowing, osteophyte and cyst formation and subchondral sclerosis, where available
- 5) MRI analysis of bone marrow lesion variables, where available
- 6) Incidence and time to resolution of post-operative complications and adverse events
- 7) Incidence and time to joint injections, where available
- 8) Incidence and time to re-operations and revisions
- 9) Number of visits to healthcare providers, diagnostic or treatment procedures, and support devices; use of pain medication; and days of productivity lost, where available

7.0 Study Design

This is a multicenter, prospective, single-blinded, two-arm, randomized study. Enrolled subjects will have a single BML of the tibia, single BML of the femur, or adjoining BMLs of tibia and femur, as long as the BMLs are in the same compartment of the knee. Subjects will also be surgical candidates for knee arthroscopy due to mechanical symptoms, meniscus tear, loose body and/or synovitis.

A stratified blocked randomization will be used to assign subjects to either Subchondroplasty with arthroscopy or to arthroscopy alone in a 2:1 ratio. Individual sets of blocks will be determined within study site and lesion polarity status (unipolar vs bipolar).

Subjects will be consented within 90 days prior to surgery and take part in follow-up visits for two years following surgery. A preoperative visit (with exception of MR imaging) will occur within 60 days prior to surgery. Telephone follow-up interviews will be done at 6 weeks, 3 months, 6 months, 9 months, 18 months and 24 months post-surgery. Target enrollment is 201 subjects, to include 134 subjects in the treatment group (SCP + Arthroscopy) and 67 subjects in the control group (Arthroscopy alone).

Enrollment was stopped early when an interim analysis demonstrated that the study was unlikely to meet its primary endpoint due to an unexpectedly high success rate in the arthroscopy only group. Follow-up will continue for all subjects enrolled through the 24 month visit to allow further monitoring of outcomes related to revisions, reoperations, adverse events, and to collect KOOS assessments and numeric pain scores.

Subjects will complete the study at the 24 month follow-up visit. For the purposes of this protocol, a revision will be defined as any partial or total joint arthroplasty or any bone fixation, bone grafting or bone substitute procedure in the same compartment in the study knee.

8.0 Subject Selection Criteria

8.1 Inclusion Criteria

Candidates must meet ALL of the following:

- 1) Voluntary signature of the IRB/REB approved Informed Consent,
- 2) Male or female subjects between the ages of 30 to 75 years,
- 3) Body Mass Index ≤ 40 (BMI=kg/m²),
- 4) Has experienced pain in study knee for at least 3 months,
- 5) Kellgren-Lawrence grade 1-3 Osteoarthritis in the study knee, as reviewed on preoperative XR imaging,
- 6) BML is confirmed on T2 weighted or Proton Density MR Imaging by presence of white signal,
- 7) Single BML of tibia, single BML of femur, or adjoining BMLs of tibia & femur, in the same compartment, extending to the articular surface of the joint,
- 8) Surgical candidate for knee arthroscopy due to mechanical symptoms, meniscus tear, loose body and/or synovitis,
- 9) Must record a response, at the preoperative study visit, of moderate to extreme pain for any one of the KOOS Pain Scale questions, P2 through P9,
- 10) Index knee alignment is defined radiographically as one of the following: Neutral, \leq to 6° mechanical varus, or \leq 6° mechanical valgus,
- 11) Ligaments in the study knee are stable,
- 12) The contralateral (non-study) knee is stable and functional,
- 13) Is refractory to conservative non-surgical management
 - a) having failed 2 or more of the following: hyaluronic acid injection, corticosteroid injection, NSAIDs, physical therapy, bracing, activity modification, or minimal surgical intervention (e.g., arthroscopy, debridement/chondroplasty, and/or loose body removal)
 - b) and is ≥ 3 months from the start of treatment (these treatments can continue up to the time of the randomized procedure; injections to be completed per Section 10.4.7),
- 14) Must be physically and mentally willing and able, in the Investigator's opinion at the time of enrollment, to be compliant with the protocol, including all follow-up visits, survey completion, weight-bearing restrictions, and post-operative rehabilitation.

8.2 Exclusion Criteria

Candidates will be excluded if they meet ANY of the following:

- 1) BML caused by acute trauma less than 3 months prior to enrollment,
- 2) Clinical and/or radiographic disease diagnosis of the index knee that includes any of the following:
 - a. Kellgren-Lawrence Grade 4 Osteoarthritis with complete loss of joint space (bone-on-bone) or subchondral bone collapse,
 - b. Rheumatoid arthritis, or history of septic or reactive arthritis,
 - c. Gout or a history of gout or pseudogout in the affected knee,
 - d. Has more than two clinically relevant BMLs in the index knee,
 - e. Osteochondritis dissecans of the knee with significant bone loss,
 - f. Collapse of subchondral bone,
 - g. Clinically relevant BML located at ACL/PCL insertion,
 - h. MRI evidence of frank ligament instability,
- 3) Passive knee flexion $< 110^{\circ}$ or flexion contracture $> 30^{\circ}$,
- 4) History of systemic diseases which could contribute to secondary arthropathies (e.g., sickle cell disease, hemochromatosis, or autoimmune disease),
- 5) Has a neuromuscular, neurosensory, or musculoskeletal deficiency that limits the ability to perform objective functional assessment of either knee,
- 6) If diabetic, blood glucose over 200 mg/dL at time of enrollment,
- 7) Current daily tobacco or high nicotine product user or < 3 months from nicotine cessation,
- 8) Presents a high surgical risk due to unstable cardiac and/or pulmonary disease,
- 9) Has HIV or other immunodeficient state including subjects on immunosuppressant therapies, or has significant illness (metastasis of any type) that decreases the probability of survival to the 2 year endpoint,
- 10) Is at substantial risk for the need of organ transplantation, such as renal insufficiency,
- 11) Is pregnant or breast-feeding at the time of surgery,

- 12) Has a history of any invasive malignancy (except non-melanoma skin cancer), unless treated with curative intent and with no clinical signs or symptoms of the malignancy for 5 years,
- 13) Has primary bone tumor in the knee area,
- 14) Anticipates having a lower extremity surgery other than the investigational surgery during the course of the study
- 15) Is participating concurrently in another clinical trial, or has participated in a clinical trial within 30 days of surgery,
- 16) Is receiving prescription pain medication other than NSAIDs or acetaminophen for conditions unrelated to the index knee condition, chronic use of anticoagulants, or taking oral or inhaled corticosteroids,
- 17) Active joint infection or history of chronic joint infection at the surgical site,
- 18) Prior total meniscectomy of index knee,
- 19) Has primarily patellofemoral symptoms,
- 20) Is indicated for concomitant procedures (i.e., microfracture, subchondral drilling, cartilage allograft, ligament or tendon repair, distal realignment/osteotomy, root repair) in the index knee, with the exception of incidental loose body removal, debridement, synovectomy, osteophyte removal in locations other than adjacent to BMLs, and/or partial meniscectomy,
- 21) Has contraindications for Magnetic Resonance Imaging (MRI),
- 22) Is receiving worker's compensation or currently involved in litigation relating to the index knee,
- 23) Has a history of substance abuse.

9.0 Study Procedures

9.1 Screening and Enrollment

Potential subjects will be screened from each investigator's subject population. Subjects in this group will be screened for eligibility based on the inclusion and exclusion criteria described in Sections 8.1 and 8.2. The Study Site will maintain a Subject Screening Log to track all screened subjects, including subjects who do not meet the study criteria and those who decline to participate. For subjects who do not meet the study criteria, the reason for ineligibility will be recorded on the log; however, their eligibility criteria should not be entered into the Electronic Data Capture (EDC) System.

Subjects will not be invited to participate in the study until after approval of the protocol by the reviewing IRB/REB. Subjects will be considered enrolled in the study if they meet

the pre-surgery inclusion and exclusion criteria, sign a consent form, and undergo a randomized study procedure. The Study Site will maintain a Subject Enrollment Log for all enrolled subjects.

9.2 Informed Consent

All study subjects are required to undergo the process of Informed Consent and sign an Institutional Review Board (IRB) or Research Ethics Board (REB) approved Informed Consent Form, compliant with 21 CFR Part 50-Protection of Human Subjects, and in accordance with institutional policies. The Informed Consent Form must be signed prior to the conduct of any protocol-specific procedures or data collection. Informed consent may be obtained up to 90 days prior to surgery.

If the Study Site does not have an IRB/REB of record, a central IRB/REB may be utilized upon approval by Zimmer Biomet.

9.3 Preoperative Procedures

Preoperative procedures include a knee examination, documentation of medical and knee history and pain medication use, collection of baseline X-rays, and completion of subject-reported outcomes surveys. All preoperative procedures are to be completed within 60 days prior to the study surgery; this includes X-ray images. A preoperative MRI will also be included in the study analysis. The MR images may be obtained up to 90 days prior to surgery and according to the Image Acquisition Protocol (Appendix C). The Schedule of Events is listed in **Table 1**.

9.3.1 The knee examination is to be conducted during a preoperative visit including evaluations of laxity, alignment, range of motion, effusion and passive motion deficit as appropriate for the subject's condition.

9.3.2 The preoperative visit will also include collection of basic demographic information and medical history, current use of prescription and over-the-counter pain medication, and a detailed history of all knee-related injuries, treatment and surgeries.

9.3.3 A baseline series of knee x-rays are to be obtained prior to surgery. This series is to include:

- Long Standing AP View
- Lateral View
- PA Fixed Flexion (Bilateral) View
- Skyline/Sunrise View

The Image Acquisition Protocol (Appendix C) describes the views and parameters in detail.

The preoperative x-ray files are to be submitted to the central imaging laboratory, per the Image Transfer Protocol (Appendix D).

9.3.4 The Institution's MRI Department is to obtain the preoperative images

described and prepare the standard imaging report within 90 days prior to the surgery. The investigator shall obtain a copy of this report and the images. The MRI files are to be submitted to the central imaging laboratory per the Image Transfer Protocol (Appendix D).

MR examinations are to be performed on a 1.5 or 3.0 T MR. The following sequences are to be applied:

- Three Plane Localizer
- Coronal Proton Density Sequence with Fat Saturation
- Coronal Short Tau Inversion Recovery (STIR)
- Sagittal T1 Weighted
- Sagittal Proton Density Sequence with Fat Saturation
- Sagittal 3D SPGR (Spoiled Gradient) Sequence with Fat Saturation
- Axial Proton Density Sequence with Fat Saturation

The Image Acquisition Protocol (Appendix C) describes the examination protocol in detail. If the institution utilizes an MR device that is not listed on or compatible with the Image Acquisition Protocol, Zimmer Biomet will arrange for an alternate protocol to be provided by the central imaging laboratory.

9.3.4 The subject is to complete a series of surveys and scales regarding their clinical outcomes at the time preceding surgery, including pain, range of motion, and activities. These scales include:

- The Knee Injury and Osteoarthritis Outcomes Score (KOOS)
- EQ-5D
- Numeric Pain Scale
- Healthcare Utilization Survey

9.3.5 Use of any preoperative injections within the past year into the index knee should be recorded on the Healthcare Utilization Form during the baseline visit. Potential subjects can continue to receive injections preoperatively, with no washout period. Injections however should not be given within 2 weeks prior to the baseline visit and if given, should be done after completion of subject reported outcome forms.

9.4 Randomization Procedures

The surgeon will be blinded to the treatment group until the time of surgery to avoid potential selection bias during the screening process. The subject will be blinded to the treatment group throughout the study. The research coordinator will input the subject's Inclusion/Exclusion criteria into the Electronic Data Capture System, once all criteria has been confirmed, and select that the subject is ready to randomize when appropriate. Subjects may be randomized prior to surgery to allow for OR set-up. However, randomization should be performed as close to the time of surgery as possible to reduce the risk of randomization failures due to cancelled procedures.

9.5 Operative Procedures

9.5.1 Arthroscopy Control Procedure

All operative procedures are to be performed under aseptic conditions according to the institution's standards. After randomization, subjects assigned to the Arthroscopy control group will undergo arthroscopy of the study knee with one or more of the following procedures:

- Partial meniscectomy
- Lavage
- Debridement
- Loose body removal
- Synovectomy
- Removal of osteophytes in the notch or locations other than those adjacent to BML(s)

No cartilage repair procedures other than debridement should be performed. Osteophytes adjacent to the target BML(s) identified on MRI should not be treated. Additionally, for subjects with meniscal root injuries, root repairs should not be performed.

Superficial skin incision(s) should be created at the typical AccuPort® access point(s) as if the subject had undergone SCP. The incisions should be closed in the typical fashion.

9.5.2 Subchondroplasty Procedure

After randomization to the study group, subjects assigned to the SCP + Arthroscopy group will undergo the Subchondroplasty portion of the procedure before or after the Arthroscopy portion per the surgeon's discretion. All operative procedures are to be performed under aseptic conditions according to the institution's standards. The same Arthroscopic procedures reported above for Arthroscopy Control subjects should be performed for Subchondroplasty + Arthroscopy subjects. The Subchondroplasty surgical technique is described in detail in Appendix B, with the required steps outlined below.

- The preoperative MRI should be used in planning the access point, trajectory and depth of the AccuPort® cannula(s) for accessing the location of the BML(s).
- AccuPorts should be placed using fluoroscopic guidance.
- Use of the SCP Navigation guide is optional.
- AccuFill should only be mixed with saline, for consistency between subjects.
- Appropriate volume of AccuFill should be used to adequately fill the area(s) of BML(s) taking care not to over-pressurize or overfill the defect. Multiple fluoroscopic images should be taken during injection to check for extravasation of material.
- Any extravasation of material into surrounding soft tissues should be

thoroughly irrigated at the time of the procedure.

- An arthroscopic examination of the joint should be performed after injection to check for any material in the joint space. Any material found should be evacuated from the joint utilizing suction and lavage.

9.5.3 Surgical Documentation

The investigator is to dictate detailed operative notes that include the measures listed below, or have paper copies of the Surgical Documentation Case Report Forms completed during surgery to serve as source documents. Arthroscopic and Fluoroscopic images should also be retained in the study files.

Surgical Documentation

- Randomization Allocation
- OR Time
- SCP Procedure Time (if applicable)
- Anesthesia Type
- Intraoperative Adverse Events
- Documentation of Cartilage Lesions
 - Location: femur, tibia, or patella; surface;
 - ICRS Grade
 - Lesion Size, if ICRS Grade 3 or 4
- List of Concomitant Arthroscopic Procedures
- Documentation of Remaining Meniscus Status
- Documentation of SCP Injection (if applicable)
 - Type of AccuPort(s) used (end target, side target, etc.)
 - Volume of AccuFill injected
- Part and Lot numbers of AccuFill, AccuPort(s) and AccuMix used (if applicable)

9.6 Perioperative Pain Management, Postoperative Procedures and Assessments

Perioperative pain management is important in maintaining blinding of subjects. Perioperative pain management protocols may be determined per investigator and institution preference but should be consistent between treatment groups at each site to ensure subject blinding.

During the immediate postoperative period, the investigator's standard postoperative care procedures should be followed. All adverse events and complications are to be assessed and recorded on the **Adverse Event Form**, per Section 11.0 Safety Management—Medical Events/Adverse Events.

Rehabilitation should be performed as part of a 3 to 6 month program, depending on the progress of the individual subject. The Recommended Rehabilitation Protocol is found in Appendix E.

9.7 Telephone Follow-Up Interviews

Telephone follow-up interviews are scheduled at 6 weeks, 3, 6, 9, 12, 18 and 24 months following the date of surgery. Each interview will include screening for Adverse Events, Serious Adverse Events, and reoperations that have occurred since the last follow-up interval and completion of a subset of subject reported outcomes surveys..

A Subject Stipend may be offered to the subject at the completion of each follow-up visit, if in accordance with the institution's policies, and if the subject has completed the full visit, Sections 9.7.1 – 9.7.2. The stipend is provided to defray costs of travel, parking and missed time from work.

Follow-up visits are detailed in **Table 1. Schedule of Events**. All visits are to occur within the windows described in **Table 1**.

9.7.1 Subject Reported Outcome Surveys

The study's Electronic Data Capture System can be configured to send an email notification to subjects at the beginning of each visit window with a reminder that they need to complete the KOOS Pain Scale or KOOS and Numeric Pain Scale surveys. This email will contain a method to allow the subjects to complete their surveys electronically via the EDC's electronic subject reported outcomes (ePRO) system. Prior to conducting the phone interview, the Study Coordinator will check to confirm whether these surveys have been completed electronically or not. If they have not been completed, the Study Coordinator will fax, email or mail a copy of the applicable surveys to the subject with instructions for completion or initiate another reminder from the ePRO system. Mailed surveys will be sent with a stamped, return envelope. Any subject survey forms that are not collected via the database's ePRO system are to be maintained in the subjects' study files as source documents.

9.7.2 Telephone Interviews

The Study Coordinator will schedule a call with the subject within the visit window. During the call, the subject is to be queried regarding the occurrence of any Adverse Events and Serious Adverse Events, per Section 11.0 Safety Management—Medical Events/Adverse Events. Any adverse event that results in reoperation or revision is to be recorded as a Serious Adverse Event.

The subject is to be queried regarding any reoperations of the index knee. All reoperations are to be documented using the Surgical Reoperation Form, per Section 10.4.2.

If the subject has not already completed the applicable PROs, these subject reported outcome surveys may be completed during the telephone interview. The Study Coordinator is to read each question and record the answer given.

The Study Coordinator is to document the phone interview, including any completion of outcome measures over the phone, in the subjects' study files.

Table 1. Schedule of Events

	Visit 1	Visit 2	Visit 3	Visit 4	Visit 5	Visit 6	Visit 7	Visit 8	Visit 9
Procedures	Study Admit/ Pre-operative	Operative	6 Weeks	3 Months	6 Months	9 Months	12 Months	18 Months	24 Months
Visit Window	≤60 days Prior to Surgery		±10 Days	±30 Days	±30 Days	±30 Days	±2 Mos	±2 Mos	±2 Mos
Informed Consent ¹	X								
Inclusion & Exclusion Criteria	X								
Demographic Form	X								
Knee Examination	X								
Knee History	X								
Medical History	X								
Pain Medications	X								
X-Ray Series	X								
MRI ¹	X								
Telephone Follow-Up			X	X	X	X	X	X	X
Screen for Adverse Events ²		X	X	X	X	X	X	X	X
KOOS Knee Survey	P		P	P	P	P ³	P	P	P
Numeric Pain Scale	P		P	P	P		P	P	P
EQ-5D	P								
Healthcare Utilization	P								
Return to Work									
Surgical Documentation		X							
Serious Adverse Event ²		(X)	(X)	(X)	(X)	(X)	(X)	(X)	(X)
Protocol Deviation ²		(X)	(X)	(X)	(X)	(X)	(X)	(X)	(X)
Surgical Reoperation ⁴			(X)	(X)	(X)	(X)	(X)	(X)	(X)
Study Exit ⁵		(X)	(X)	(X)	(X)	(X)	(X)	(X)	(X)

X Investigator completed forms

P Subject completed forms

¹Informed Consent and Baseline MRI to be done within 90 days of study enrollment.

² Case Report Forms to be completed if/when event occurs.

³ KOOS Pain Subscale *only* at 9 month visit

⁴ Surgical Reoperation form will be completed if the investigator performs any procedure on the index knee regardless of whether the subject's change in condition is related to the initial study procedure.

⁵ Study Exit form will be completed if the subject is no longer participating in the study for any reason.

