17.0 Data Handling and Record Keeping

17.1 Data Collection

Data will be recorded using an electronic data capture (EDC) platform provided by Zimmer Biomet. Zimmer Biomet personnel will provide access, training and user support to all sites. Investigative sites will be required to have broadband internet access with standard firewall protection features.

Data are to be recorded utilizing subjects' source documentation, which includes medical records, operative and clinic notes, ancillary services reports, subject surveys and in some cases Case Report Forms. The subject-completed surveys are considered source documentation for this information. This may include electronically collected ePRO surveys where the direct data entry of survey data by the subject constitutes electronic source, paper surveys completed and submitted by the subject, or paper surveys completed on behalf of the subject by the site coordinator during phone interviews. Case Report Forms or certified copies of Case Report Forms may also serve as source documentation when the information is in addition to what is typically entered into a subject's medical record (e.g. fields documenting SCP time on the Surgical Documentation Form). Any Case Report Forms used as source documentation are to be labeled as such and made part of the subjects' case histories. Data are to be recorded accurately and in a timely manner following each event.

Questions regarding the content of the forms should be directed to the Zimmer Biomet Study Representatives.

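### The KOOS may be read out and recorded by telephone by a coordinator whom no rule blinds, so part of the CCS pain component may be collected by someone who knows the arm

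*Combined protocol and SAP*

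**What the plan says.** Section 7.0 describes the design: "This is a multicenter, prospective, single-blinded, two-arm, randomized study". Section 9.4 sets out who is blinded. For the subject: "The subject will be blinded to the treatment group throughout the study". For the surgeon: "The surgeon will be blinded to the treatment group until the time of surgery to avoid potential selection bias during the screening process". No section blinds the coordinator or asks for a blinded interviewer.

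Table 1 marks the KOOS with the code "P Subject completed forms". For follow-up, Section 9.7.1 puts self-completion first: an ePRO email where configured, a check by the coordinator before the call, then a faxed, emailed or mailed form or another ePRO reminder. Section 9.7.2 adds a fallback: "If the subject has not already completed the applicable PROs, these subject reported outcome surveys may be completed during the telephone interview". In that case, "The Study Coordinator is to read each question and record the answer given". The coordinator must note in the study files any outcome measure completed by telephone. Section 17.1 lists as source data "paper surveys completed on behalf of the subject by the site coordinator during phone interviews".

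On access to the allocation, Section 9.4 has the research coordinator enter eligibility in the EDC and "select that the subject is ready to randomize when appropriate", possibly ahead of surgery so that the operating room can be prepared. The surgical documentation in Section 9.5.3 includes the allocation and the AccuFill volume. Section 17.2 gives the site coordinator the task of making corrections in the EDC.

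**The concern.** CCS requires freedom from SSSI and, among subjects free from it, a gain of at least 10 points in KOOS pain (Section 14.1). The pain part is a self-report cut at a threshold, so a small influence on answers can move a subject who lies near the line. An interviewer who knows the arm could exert such influence without intending to, through tone, prompting or the choice between two adjacent answers. The same call also covers adverse events and reoperations, which could colour the KOOS answers if asked first, and a subject might pick up cues about the arm.

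If such influence differed by arm, it would bias the primary comparison, and neither the one-sided test nor the Bonferroni split would protect against it. Section 10.4.5 shows that the sponsor uses masking where it sees a risk: material for the independent cross-over review must not reveal the arm. No similar safeguard covers the collection of the KOOS scores themselves.

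**Working it through.** **Step 1. Is the procedure allowed, and by whom?** Sections 9.7.2 and 17.1 both allow read-out by a coordinator. Neither limits it to particular visits, so months 12 and 24 are included. The synopsis (Materials and Methods) presents telephone collection and ePRO as alternative routes, and no section caps the telephone share.

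**Step 2. Does any rule keep the interviewer unaware of the arm?** No. Blinding covers the subject and, until surgery, the surgeon. The coordinator's duties in Sections 9.4 and 17.2, and the content of the surgical record in Section 9.5.3, make knowledge of the arm possible. No section says that it occurs.

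**Step 3. Reproduce the plan's own figure.** Inputs from Sections 14.2 and 14.5: rates 0.60 and 0.80, 2:1 allocation, one-sided test, 80% power; alpha 0.04 (month 24).

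- Pooled rate: (0.60 + 2 × 0.80)/3 = 0.7333.
- Uncorrected control n = [1.7507 × √(1.5 × 0.7333 × 0.2667) + 0.8416 × √(0.24 + 0.16/2)]² / 0.20² = 50.71.
- With continuity correction: (50.71/4) × [1 + √(1 + 2 × 1.5/(50.71 × 0.20))]² = 57.97, so 58 control and 116 treated, 174 in total. This matches the plan.

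Blinding the interviewer would not change this number.

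**Step 4. Illustrate what a one-sided influence would do.** The documents do not give the share of KOOS forms read out (f) or the net share of those moved from failure to success in S+A (b). Both are assumed. With no true effect, CCS is 0.60 in AA and 0.60 + d in S+A, where d = f × b.

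P(reject) = Φ[(d − z × SE₀)/SE₁], where SE₀ uses the pooled rate, SE₁ the separate rates, n = 116/58, and z is the one-sided critical value (1.7507 for alpha 0.04).

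Example for d = 0.04: pooled rate = (58 × 0.60 + 116 × 0.64)/174 = 0.6267, SE₀ = 0.0778, SE₁ = 0.0783, and P = Φ[(0.04 − 1.7507 × 0.0778)/0.0783] = about 0.110.

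| f × b | Shift in S+A | Alpha 0.04 (month 24) | Alpha 0.01 (month 12) |
|---|---|---|---|
| none | 0 | 4.0% | 1.0% |
| 10% × 5% | 0.5 point | 4.6% | 1.2% |
| 20% × 5% | 1 point | 5.2% | 1.4% |
| 20% × 10% | 2 points | 6.8% | 1.9% |
| 40% × 10% | 4 points | 11.0% | 3.6% |

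**Step 5. How demanding are these inputs?** At CCS 0.60, 40% of read-out scores would be failures. Moving 10% of all read-out scores means moving 0.10/0.40, or one in four of the S+A failures, with no movement in AA. Moving 5% means one in eight. The upper rows therefore describe a substantial influence.

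**The case against.** A reader might infer that interviewers do know the arm. The documents do not say so. Marking a subject as ready to randomise starts the process but is not receipt of the result. The titles research coordinator, Study Coordinator and site coordinator are never said to mean one person, although nothing keeps the roles apart. Knowledge of the arm is possible, not established.

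Read-out is also a fallback: Section 9.7.1 puts ePRO and paper first, and Section 9.7.2 already requires telephone completion to be noted, so the mode can be traced. The respondent is blinded and control subjects receive matching skin incisions (Section 9.5.1), which limits expectation effects. All of this stands. It lowers the likely size of any bias, but does not remove the route by which an interviewer could influence the answer.

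The figures rest on assumptions. They use the planned 116/58, but enrolment stopped early and final numbers are not given. With an assumed 60/30 evaluable, shifts of 2 and 4 points give about 6% and 8.5% at alpha 0.04. Influence could also run against S+A. A reader should not take 11% as an estimate for this trial.

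A further tempting reading is that a self-completed baseline followed by telephone scores biases the comparison by itself. It would do so only if telephone use or its effect differed by arm, and the documents give no reason to expect that among blinded, randomised subjects.

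**Conclusion.** The concern holds in limited form. The plan allows a coordinator whom no rule blinds to take the KOOS by telephone at the visits that decide CCS, so part of the subjective component may be collected by someone aware of the arm. That it is so collected, how often, and in which direction any bias would run cannot be settled from the documents. If a net 0.5 to 4 points of CCS were added in S+A alone, with 116/58 evaluable and a common rate of 0.60, the false-positive rate would be roughly 4.6–11% instead of 4% at month 24; shifts of 1 to 4 points would give about 1.4–3.6% instead of 1% at month 12. The weakness is cheap to reduce. No analysis by mode of completion is planned, so without a change readers could not judge whether it mattered.

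**What to change.** **Collection (Section 9.7.2).** For surveys still outstanding at the call, have the subject complete the ePRO link during the call or return the paper form already provided for in Section 9.7.1. Keep coordinator read-out as a last resort, read verbatim, before the adverse event and reoperation questions, and where feasible by existing staff who have not seen the allocation. This last condition should not be absolute, because the documents do not show that every site has such staff.

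**Data.** Turn the telephone-completion note already required into a mode-of-completion field for every KOOS, and report mode by arm and visit.

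**Analysis (Section 14.9).** Before data lock, specify a supportive CCS sensitivity analysis by mode at months 12 and 24, for example treating read-out scores as missing under the existing methods. Leave the primary analysis unchanged.

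**Cost.** Protocol wording, one data field and one extra analysis; no added visits. A few paper forms may come back late. Setting observed scores aside lowers precision and may cross the 10% trigger for multiple imputation, but only within the sensitivity analysis. Recruitment ended in November 2020, so the change in collection reaches only the remaining follow-up visits; the mode field can be back-filled from the study files.
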